## **6.5 POOLING OF CENTRES**

It is planned that up to 10 patients in approx. 7 centres in 7 countries will be entered in this trial, i.e., it can be expected that 1 or 2 patients only will be entered per centre. All endpoints will be evaluated by descriptive statistical methods, unless otherwise specified.

Given the low number of patients per centre and the primarily descriptive nature of statistical analysis, separate analyses by centre are not meaningful and not desirable. All patients from all centres will be pooled for statistical analysis.

Listings, sorted by centre, will however be displayed.

## **6.6 HANDLING OF MISSING DATA AND OUTLIERS**

### **6.6.1 Withdrawals**

**CTP:** *If a patient is removed from or withdraws from the trial prior to the administration of trial medication, the reason for withdrawal will be entered in the case report form (CRF) and trial database and will be reported in the clinical trial report (CTR). If a patient is removed from or withdraws from the trial after the administration of trial medication, this will be documented and the reason for discontinuation must be recorded in the CRF. The data will be included in the CRF/trial database and will be reported in the CTR.*

## **6.6.2 Efficacy data**

Handling of missing item scores for the FACIT will be based on FACIT Administration and Scoring Guidelines (Version 4): If there are missing items in the FACIT-Fatigue, the FACIT-Fatigue scale score can be prorated. This is done by multiplying the sum of the FACIT-Fatigue scores by 13 (i.e. the number of items in the FACIT-Fatigue scale), then dividing by the number of items actually answered. When there are missing data, prorating in this way is acceptable as long as more than 50% of the items were answered, i.e., if the number of answered questions is 7 or higher. Cf. [Section 9.1](#) for details regarding the derivation of the FACIT-Fatigue scale score.

For the GPPASI, GPPGA and PSS total scores, a missing item or component score will lead to a missing total score. However, individual items and subscores may be presented as applicable. Cf. Section 9.1 for further details regarding the derivation of efficacy endpoints.

Based on the different reasons for patients' data missing for different endpoints, various approaches will be used to assess the impact of missing data on the efficacy endpoints of this trial, depending upon the type of the endpoint (cf. [Table 6.3: 1](#)). Approaches to be applied are described below.

Note that Visit 14 (i.e. the Week 20 (follow-up)) is intended to report follow-up data, i.e., data collected after the end of the on-treatment period (as defined in [Table 6.1: 1](#)). Therefore, no imputation based on data from the on-treatment period will be used to impute missing data at Visit 14 in order to avoid the mixing of on- with off-treatment data.

For the final analysis on the 4-week data, missing data imputations will be performed using only the data cleaned and planned to be reported at this time ([Table 6.7: 1](#)); data from later time-points will be excluded.

### Binary efficacy endpoints

Some efficacy endpoints are defined in terms of the proportion of patients with a particular binary outcome, i.e. achievement of a GPPGA total score of 0 or 1. For those binary outcomes, the different methods for handling of missing data, presented below, will be performed as presented in Table 6.3: 1. Please note that some of these binary outcomes are derived from other parameters, but imputation is planned to take place only at the binary level, i.e., the GPPGA total score itself will not be imputed, but the binary endpoints derived based on these scores will be imputed.

- The following primary imputation strategy ("NRI") will be performed:
  - If there are data at the visits both immediately before and immediately after the visit with a missing outcome, then impute as success only if both the preceding and the following observations also represent a success (independent of whether the preceding and following observations were selected for analysis based on time windows described in [Section 6.7](#));
  - Otherwise, impute as a failure to achieve a response (i.e. no response imputation [NRI]).

For patients who take a rescue medication (as defined in [Section 5.3.4](#)) during the course of the study, all efficacy outcomes measured after the day of first use of rescue medication will be set to missing and, during the on-treatment period, will be imputed using the steps described above.

- Observed cases (OC) approach will be used as a sensitivity analysis and will include all collected data, with no imputation performed on the missing data. Such an OC approach will exclude all values measured after intake of a rescue medication (i.e. such values will be set to missing).
- Observed cases including rescue (OC-IR) approach will be used as a further sensitivity analysis and is an extension of the OC approach which includes additionally all values which were measured after rescue medication intake.

#### Continuous efficacy endpoints

For continuous efficacy endpoints, such as the pain VAS, FACIT-Fatigue scale score, and GPPASI total score, the different methods for handling of missing data, presented below, will be performed as presented in [Table 6.3: 1](#):

- Imputation technique ("LOCF"): Under the assumption that the disease is self-limiting and will gradually improve over time, the LOCF approach will be used as the primary imputation strategy to replace missing values either at intermediate visits or due to early withdrawal from the trial. The last available value, including baseline, will be carried forward to all subsequent visits within the on-treatment period at which a measurement is missing. Values measured after the day of first rescue medication intake (as defined in [Section 5.3.4](#)) will be set to missing and the missing values within the on-treatment period will be imputed by LOCF.
- In addition, as sensitivity approaches, the OC and OC-IR will also be performed.

#### Rescue medication use

The original results (OR) approach implies the presentation of data exactly as observed (not using time windows as described in Section 6.7 and not setting values to missing).

OR analysis will be performed on parameters and endpoints that are either not affected by patients' rescue medication use (e.g. plasma concentration level of BI 655130, rescue

medication use itself), or, if it is not meaningful to apply any imputation rule for the replacement of missing values.

### **6.6.3 Safety data**

**CTP:** *With respect to safety evaluations, it is not planned to impute missing values.*

The only exceptions where imputation might be necessary for safety evaluation are AE dates and start and stop dates for concomitant medications. Missing or incomplete AE dates are imputed according to BI standards (see 001-MCG-156\_RD-01 (4)).

Partial start and stop dates for concomitant medications and historical medication for GPP will be imputed to enable subsequent calculation (but not for display) by the following "worst case" approach:

- If the day of the end date is missing, then the end date is set to last day of the month (or to the patient's trial completion date, if it is earlier than the last day of the month).
- If the day and month of the end date are missing then the end date is set to 31st of December of the year (or to the patient's trial completion date, if it is earlier than the 31st of December of the year).
- If the day of the start date is missing the start date is set to first day of the month (except for rescue medication, where the first dosing day will be used if first dosing happened in the same month).
- If the day and month of the start date are missing then the start date is set to 1st January of the year (except for rescue medication, where the first dosing day/month will be used if first dosing happened in the same year).
- All other cases need to be assessed by the trial team on an individual basis, using the above points as guidance.

If a concomitant medication or historical medication was ticked to be ongoing, it is expected that the end date is missing and will not be imputed for display purposes.

For safety data that are displayed by time point (or visit) of measurement, the OC-IR approach will be used.

### **6.6.4 PK data**

Missing data and outliers of PK data are handled according to BI standards (see 001-MCS-36-472\_RD-01 (5)). **CTP:** *Drug concentration data identified with NOS (no sample available), NOR (no valid result), NOA (not analyzed), BLQ (below the lower limit of quantification), or NOP (no peak detectable) will be displayed as such and not replaced by zero at any time point (this rule also applies [...] to the lag phase, including the predose values).*

**CTP:** *For the non-compartmental analysis, concentration data identified with NOS, NOR or NOA will generally not be considered. Concentration values in the lag phase identified as BLQ or NOP will be set to zero. All other BLQ/NOP values of the profile will be set to*

*missing. The lag phase is defined as the period between time zero and the first time point with a concentration above the quantification limit.*

PK data will be presented using the OR approach described in [Section 6.6.2](#).

#### **6.6.8 Time since first diagnosis**

For incomplete information on the date of first diagnosis, time since first diagnosis will be calculated as follows:

- If the year of first diagnosis is unknown, time since first diagnosis will be set to missing.
- If day and month of the first diagnosis are unknown, time since first diagnosis will be calculated as if diagnosed on the 30th June of that year.
- If only the day of the first diagnosis is unknown, time since first diagnosis will be calculated as if diagnosed on the 15th of that month.

### **6.6.9 Disease characteristics**

Incomplete information regarding disease characteristics will be imputed as follows:

- If the "number of flares of GPP that resolved spontaneously without treatment" is  $>0$  and equal the "number of resolved flares of GPP (total)" in previous 12 months, and information is missing whether the shortest flare resolved spontaneously without treatment, this information will be imputed with "Yes". This will be analogously done for the longest flare, but only if "number of resolved flares of GPP (total)" in previous 12 months is reported to be  $> 1$ .
- For calculation of "time since start of last flare of GPP before the trial to Visit 2", partial dates for "start date of symptoms of last flare" will be replaced with the first day of the month (if month and year are available). Otherwise, the dates will not be replaced. Replacement will only be done for calculation; the "start date of symptoms of last flare" will not be imputed.
- If the actual "start date of symptoms of last flare" is unknown but "before the 12 months that precede the trial", then the "time since start of last flare of GPP before the trial to Visit 2" will be set to " $> 1$  year" for the statistical summary of disease characteristics.
- If the actual "start date of symptoms of last flare" is unknown but "during the 12 months that precede the trial", then the "time since start of last flare of GPP before the trial to Visit 2" will be set to " $\leq 1$  year" for the statistical summary of disease characteristics. If additionally no information was provided regarding the date of resolution of last flare of GPP before the trial (i.e. no date and no time interval relative to start of trial), this will be imputed with the information that the flare stopped "during the 12 months that precede the trial".

## **6.7 BASELINE, TIME WINDOWS AND CALCULATED VISITS**

Measurements reported with date and time and taken prior to start of administration of trial treatment will be considered pre-treatment values. Measurements reported with a date only (and no time) and taken on the day of administration of trial treatment will also be considered pre-treatment values. These pre-treatment values will be assigned to visits according to the nominal visit number as recorded on the eCRF or as provided by the laboratory.

Baseline is defined as the last measurement collected prior to the start of administration of the trial treatment.

Measurements taken after start of administration of trial treatment will be considered values of the on-treatment period or follow-up values, based on the definition in [Section 6.1](#), and will be assigned to visits for statistical analysis, if applicable, as defined below.

The assessment of injection site reactions (scheduled for Visit 3 and Visit 4) will be handled differently to other by-visit endpoints, because the Visit 3 assessment is not a pre-treatment assessment, but is planned after injection of trial treatment, therefore representing an on-treatment measurement (i.e., both assessments are on-treatment assessments). Assessments at or after start of administration of trial treatment will be assigned to the nominal visit number as recorded on the eCRF, i.e. no time windows will be applied for analysis of this data.

Analysis of AE data and of rescue use will not be based on visits, therefore, no assignment to time windows will be necessary.

All other safety, efficacy and biomarker measurements will be assigned to visits based on time windows around the planned visit dates, defined relative to the day of trial treatment (which is scheduled for Visit 3). These time windows are defined in [Table 6.7: 1](#).

Table 6.7: 1 Time windows for assignment of efficacy, safety lab, vital signs, biomarker, and RNA sequencing measurements to visits for statistical analysis

Visit number	Visit label	Planned day	Time window		
			Window	Start (inclusive)	End (inclusive)
4	Week 1, Day 2	Day 2	exact day	Day 2 A	Day 2
5	Week 1, Day 3	Day 3	exact day	Day 3	Day 3
6	Week 1, Day 4	Day 4	exact day	Day 4	Day 4
7	Week 1, Day 5	Day 5	exact day	Day 5	Day 5
8	Week 1, Day 6	Day 6	exact day	Day 6	Day 6
9	Week 1, Day 7	Day 7	+ 3 days	Day 7	Day 10
10	Week 2	Day 14	+/- 3 days	Day 11	Day 17
11	Week 3	Day 21	+/- 3 days	Day 18	Day 24
For final Week 4 analysis					
12	Week 4	Day 28	- 3 days/+ 10 days	Day 25	Minimum of (cut-off B ; Day 38)
For final analysis of entire trial					
12	Week 4	Day 28	- 3 days/+ 10 days	Day 25	Day 38
13	Week 12	Day 84	+/- 14 days	Day 70	Day 98
14	Week 20 (follow-up)	Day 142 D	exact day to last value	Day 142	Day of last value C

All days are counted relative to the day of treatment, which is defined as Day 1.

A Note that measurements made at Day 1 and assigned to the on-treatment period (because mistakenly made after start of infusion of trial treatment) via assessment on date and time (i.e. safety laboratory, GPPASI, GPPGA) will not be assigned to Visit 4. Such data will be listed only.

B The cut-off date will be specified in the data cleaning plan for the 4-week analysis.

C Note that measurements assigned to the Week 20 (follow-up) visit are intended to represent follow-up measurements, i.e., made after the end of the on-treatment period (as defined in [Table 6.1: 1](#)).

D Planned day per CTP is Day 140, which would still be during the on-treatment period, as REP is defined to be 140 days.

Repeated and unscheduled efficacy, safety and biomarker measurements will be handled similarly to scheduled measurements and will also be assigned to a time window depending upon the date of measurement.

Only one observation per time window will be selected for statistical analysis at a particular visit – the value which is closest to the protocol planned visit day will be selected. If there are two observations which have the same difference in days to the planned day, but which are not measured on the same day, the later value will be selected. If there are two observations on the same day, the worst value will be selected.

Assignment of efficacy observations to visits based on time windows will be based on the non-imputed (observed) data after setting values after rescue medication intake to missing (if applicable, i.e. for the "LOCF" and "NRI" approaches and the "OC" approach defined in [Section 6.6.2](#)). Visits which were not assigned a value based on time windows will thereafter be imputed for the NRI and LOCF approaches defined in Section 6.6.2. Imputation of efficacy endpoints (binary as well as continuous) will be performed based on all available observations, irrespective of whether the observation was selected in any time window. For example, for LOCF imputation, the last observed value during the on-treatment period will be carried forward, whether or not it was the selected value in a time window. For more details on LOCF refer to Section 6.6.2.

For derivation of the last value during the on-treatment period, the minimum value during the on-treatment period, and the maximum value during the on-treatment period, all values during the on-treatment period (whether or not selected in any time window) will be considered; these will be derived for analysis of laboratory and vital signs data. For identification of potentially clinically significant abnormal laboratory values, all values (whether or not selected in any time window) will be considered.

Tables and figures with results of the statistical analysis will only display visits at which the respective parameter was planned to be collected according to the CTP.

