Name of finished product: Not applicable					
Name of active ingredient: BI 655130					
Protocol date: 22 July 2016	Trial number: 1368.11		Revision date: 09 Nov 2016		
investigator. Patients with less than 3-fold ULN increase in AST and/or ALT and/or alkaline phosphatase and/or with less than 2-fold ULN increase in total bilirubin on infusion day (V3) may be included, provided that no other cause of liver damage than GPP has been identified					
Test product: dose: mode of admin.:	BI 655130 solution for infusion 10 mg/kg Intravenous				
Comparator product: Not applicable					
Duration of treatment: Single dose					
Primary endpoint: The primary endpoint to assess safety and tolerability of BI 655130 administered intravenously, is the number [(N (%))] of patients with adverse reactions, defined as drug-related AEs.					
Secondary endpoints: 
• Percent change from baseline in GPPASI total score at Week 2• Proportion of patients with GPPGA total score of 0 (clear) or 1 (almost clear) at Week 2• Change from baseline in FACIT-Fatigue scale score at Week 2• Change from baseline in Pain VAS score at Week 2					
The following pharmacokinetic parameters will be determined as secondary endpoints: C_{max} , $AUC_{0-\infty}$					

Proprietary confidential information © 2016 Boehringer Ingelheim International GmbH or one or more of its affiliated companies

Name of company: Boehringer Ingelheim		Tabulated Trial Protocol			
Name of finished product: Not applicable					
Name of active ingredient: BI 655130					
Protocol date: 22 July 2016	Trial number: 1368.11		Revision date: 09 Nov 2016		
Further endpoints and parameters of interest:					
Criteria for safety: AEs and SAEs, safety laboratory tests, 12-lead electrocardiogram (ECG), vital signs (blood pressure [BP], pulse rate [PR], body temperature, body weight), injection site reactions, immunogenicity (ADA)					
Statistical methods: Descriptive statistics for safety, PK, and efficacy endpoints					

Proprietary confidential information © 2016 Boehringer Ingelheim International GmbH or one or more of its affiliated companies

FLOW CHART

Trial periods	Screening		Treatment	Observation											End of Trial (EOT)	
				1	1					2	3	4	8	12	16	
Week			1		1					2	3	4	8	12	16	20
Visit	1 ¹	2	3 ^{2,11}	4	5	6	7	8	9	10	11	12	12pc ³	13	13pc ³	14
Days from the day of treatment		Day-1	Day 1	D2	D3	D4	D5	D6	D7	D14	D21	D28	D56	D84	D112	D140
Time window for visits										±1d	±2d	±2d	±2d	±7d	±7d	+7d

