3. DESCRIPTION OF DESIGN AND TRIAL POPULATION

3.1 OVERALL TRIAL DESIGN AND PLAN

This single dose trial is designed as open label, exploratory, phase I, multi-centre, multi-national, single arm.

A maximum of 10 patients with a flare of GPP are planned to participate. Approximately 7 study sites in 7 countries worldwide will participate. They are all specialized referral centres experienced in the management of GPP.

Each patient will receive the active drug. Only one dose will be tested (10 mg/kg) and will be administered intravenously at Visit 3.

Patients will be hospitalized during at least 4 days following the study drug administration. Thereafter, the decision of patient's discharge will be left at the discretion of the investigator and based on the evolution of the GPP flare and the patient's health status.

Overall, 14 visits are planned. The observation period will last 20 weeks to cover the whole Residual Effect Period (refer to [section 5.2.2.2](#); Figure 3.1:1). Women of childbearing potential will perform two additional visits (phone calls) to inform the site team of the result of the urine pregnancy test at Day 56 (Visit 12pc) and Day 112 (Visit 13pc).

[figure not shown]

Figure 3.1: 1

Study design

An overview of all relevant trial activities is provided in the [Flow Chart](#). For visit schedules and details of trial procedures at selected visits, refer to [Sections 6.1](#) and [6.2](#), respectively.

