5.1.2 Assessment of efficacy

The skin condition will be assessed by using the Generalized Pustular Psoriasis Area and Severity Index (GPPASI), Generalized Pustular Psoriasis Physician Global Assessment (GPPGA) and the CGI-Improvement (CGI-I). Patients' questionnaires will also be used, fatigue scale (FACT-Fatigue), Pain VAS, Psoriasis Symptom Scale (PSS) and other relevant scores as described in [Section 5.1.1](#).

Methodological details for the evaluation of the scores/index are described in the ISF.

Generalized Pustular Psoriasis Area and Severity Index (GPPASI)

The GPPASI is an adaptation for GPP patients of the PASI, an established measure of severity and area of psoriatic lesions in patients with psoriasis [[R96-3541](#)]. Similar adaptions have been used for PPP [[R16-3360](#)]. In the GPPASI, induration component has been substituted by pustules component. It is a tool which provides a numeric scoring for patients overall GPP disease state, ranging from 0 to 72. It is a linear combination of percent of surface area of skin that is affected and the severity of erythema, pustules, and scaling (desquamation) over four body regions.

GPPASI score will be measured at Visits 3 (before study drug administration) to 10, 12 (Day 28), 13 (Day 84), and 14 (Day 140).

Generalized Pustular Psoriasis Physician Global Assessment (GPPGA)

GPPGA relies on clinical assessment of the GPP patient's skin presentation. It is a modified PGA, a physician's assessment of psoriatic lesions, which has been adapted to the evaluation of GPP patients [[R15-5200](#)]. The investigator (or qualified site personnel) scores the erythema, pustules and scaling of all psoriatic lesions from 0 - 4. Each component is graded separately, the average is calculated and the final GPPGA is determined from this composite score. A lower score then indicates a lesser severity, with 0 being clear and 1 being almost clear. To receive a score of 0 or 1, the patient should be afebrile, in addition to skin presentation requirements.

GPPGA score will be measured at Visits 3 (before study drug administration) to 10, 12 (Day 28), 13 (Day 84), and 14 (Day 140).

FACIT-Fatigue scale

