6. INVESTIGATIONAL PLAN

6.1 VISIT SCHEDULE

All patients are to adhere to the visit schedule as specified in the flow chart. Investigators should encourage patient adherence to protocol specific activities. Each visit date (with its window) is to be counted from Day 1. The acceptable time windows for observation visits and End-Of-Trial are given in the [Flow Chart](#). All deviations from the planned visit schedule will be documented. If any visit has to be rescheduled, subsequent visits should follow the original visit date schedule. Additional visits for the purpose of re-testing of laboratory parameters or AE monitoring may be included as deemed necessary by the investigator.

For planned individual plasma concentration sampling times refer to the Flow Chart. While these nominal times should be adhered to as closely as possible, the actual sampling times will be recorded and used for determination of pharmacokinetic parameters.

If a patient misses an appointment, it will be rescheduled if possible. The relevance of measurements outside the permitted time windows will be assessed no later than at the Report Planning Meeting.

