6.2.4 End-Of-Trial (Visit 14)

Completion is defined as a patient having reached the EOT visit within the specified window per the [Flow Chart](#).

Adverse events persisting after trial completion must be monitored until they have normalised or have been sufficiently characterised.

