7.6 DETERMINATION OF SAMPLE SIZE

It is planned to enter a minimum of 6 patients but allow for a maximum of 10 patients. The planned sample size is not based on a power calculation but on feasibility and practical considerations to explore safety and tolerability as well as PK and efficacy of BI 655130 in GPP patients.

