### **3. INTRODUCTION**

As per ICH E9 (1), the purpose of this document is to provide a more technical and detailed elaboration of the principal features of the analysis described in the CTP and its amendments, and to include detailed procedures for executing the statistical analysis of the primary and secondary variables and other data.

This TSAP assumes familiarity with the revised CTP. In particular, the TSAP is based on the planned analysis specification as written in CTP Section 7 “Statistical Methods and Determination of Sample Size”. Therefore, TSAP readers may consult the CTP for more background information on the study, e.g., on study objectives, study design and population, treatments, definition of measurements and variables, and planning of sample size.

Study data will be stored in a trial database within the Oracle ClinicalTM system.

The statistical analyses will be performed within the validated working environment CARE, including SASTM (current Version 9.4, by SAS Institute Inc., Cary, NC, USA), and a number of SASTM-based tools (e.g., macros for the analyses of AE data or laboratory data; Report Appendix Generator system (RAGe) for compilation/formatting of the CTR appendices).

PK parameters will be calculated using WinNonlinTM software (professional Network version 5.2, Pharsight Corporation, Mountain View, CA 94041-1530, USA).

R version 3.0.2 or later (12), Biconductor version 2.13 or later, and the limma-package version 3.18.13 or later will be used in the analyses of gene expression data. Genome version hg38/GRCh38 will be used in conjunction with Ensembl version 84 or later.

This TSAP fully specifies the planned analyses for the analysis of the 4-week data. It also specifies the planned analyses for the complete trial data through Week 20 as far as possible; prior to the final DBL, updates will be required for the analyses of further endpoints related to biomarker and RNA sequencing data.

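### The SAP's Week 20 window opens on Day 142, so an End-of-Trial visit held on the protocol's target day (Day 140) or on Day 141 enters no Week 20 by-visit summary

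*SAP*

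**What the plan says.** **Protocol.** The Flow Chart puts Visit 14 at Week 20, D140, and its row "Time window for visits" allows +7 d with no days before target. Section 6.1 fixes the counting: "Each visit date (with its window) is to be counted from Day 1". Section 5.1.2 schedules the efficacy scores on that day: "GPPGA score will be measured at Visits 3 (before study drug administration) to 10, 12 (Day 28), 13 (Day 84), and 14 (Day 140"); GPPASI has the same schedule. Section 3.1 explains the length of follow-up: "The observation period will last 20 weeks to cover the whole Residual Effect Period". Section 5.2.2.2 sets that residual effect period (REP) at 140 days. Section 6.2.4 says: "Completion is defined as a patient having reached the EOT visit within the specified window per the" Flow Chart.

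**SAP.** Section 6.7 assigns efficacy, laboratory, vital-sign and biomarker values to visits by date window, not by nominal visit number. In Table 6.7:1, Visit 13 runs from Day 70 to Day 98, and Visit 14, labelled as follow-up, runs from Day 142 to the last value. Footnote C says that Week 20 values are meant to be post-treatment. Footnote D says: "Planned day per CTP is Day 140, which would still be during the on-treatment period, as REP is defined to be 140 days". In Table 6.1:1 the REP ends 140 days after the end of infusion and follow-up starts the next day. Section 6.6.2 does not allow on-treatment data to fill a missing Visit 14. Under section 7, percentages use the whole patient set as denominator, missing values included.

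**First response.** SAP 7.5.2.1 groups the time of first GPPGA 0/1 into categories, the last running from Day 15 to Day 28. The Flow Chart permits Visit 12 on Day 28 ±2 d, and Table 6.7:1 accepts Week 4 values from Day 25 to Day 38.

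**The concern.** The protocol's last visit and the SAP's last window do not start on the same day. A patient seen exactly on schedule is a completer under protocol 6.2.4, yet contributes nothing to the Week 20 by-visit tables; a patient seen a few days late does. The protocol set the 20 weeks to span the REP, so its target day lies inside the REP by design. Treating Visit 14 as purely off-treatment therefore works against the protocol's own schedule. The SAP's tie-break also prefers the value nearest the protocol's planned day, and for Visit 14 that day is outside the window.

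In a trial of at most 10 patients, one lost assessment visibly moves a by-visit proportion or interval. Because the denominator is the full set, an observed responder seen on time counts against the Week 20 response proportion.

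The first-response list raises a related problem at Week 4. A patient whose selected Week 4 value is a first response after Day 28 is a responder in the by-visit table but has no timed category. The SAP does not say what period the no-response category covers, so two tables of one endpoint can disagree about the same patient.

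**Working it through.** **1. Reproduce the SAP's Day 142.** Both documents count treatment as Day 1, so day number = (date − infusion date) + 1. The infusion is taken to end on the day it starts.

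- Last REP day: 140 + 1 = Day 141.
- First follow-up day: 141 + 1 = Day 142.

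This matches Table 6.7:1, so the SAP is consistent with its own Table 6.1:1.

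**2. Look up each compliant Visit 14 day.** Compliant days are 140 to 147, that is 8 days.

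| Day | SAP phase | Table 6.7:1 visit |
|---|---|---|
| 140 (target) | on-treatment (REP) | none |
| 141 | on-treatment (REP) | none |
| 142–147 | follow-up | Visit 14 |

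Two of 8 permitted days are lost, including the target day; those kept are 2 to 7 days after target. Days 99 to 141 (141 − 99 + 1 = 43 days) belong to no analysis visit.

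If D140 were instead read as 140 days after dosing (Day 141), the compliant days would be 141 to 148. The target day would still be unassigned.

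**3. Effect on the GPPGA 0/1 proportion.** One responder left out of the numerator but kept in the denominator costs 1/n:

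- n = 10: 1/10 = 10.0 points
- n = 8: 1/8 = 12.5 points
- n = 6: 1/6 = 16.7 points

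The range of n comes from protocol 7.6: "It is planned to enter a minimum of 6 patients but allow for a maximum of 10 patients". SAP section 3 hopes for 8 to 10 treated patients, so 10.0 to 12.5 points is the likelier range.

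**4. Effect on the GPPASI interval.** SAP 7.5.2.1 uses mean ± t(0.975, n−1) × SD/√n. With SD held equal, the half-width is proportional to t(0.975, n−1)/√n.

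| Patients | Factor before | Factor after | Ratio | Widening |
|---|---|---|---|---|
| 10 to 9 | 0.7154 | 0.7687 | 1.075 | 7.5% |
| 8 to 7 | 0.8360 | 0.9248 | 1.106 | 10.6% |
| 6 to 5 | 1.0494 | 1.2417 | 1.183 | 18.3% |

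**5. First response.** Visit 12 is permitted on Days 26 to 30 (5 days). Days 29 and 30, 2 of 5, have no timed category. Days 31 to 38 matter only when they supply the selected Week 4 value.

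**The case against.** The strongest reply is that this is a stated rule, not a slip. Footnotes C and D, section 6.6.2 and footnote 2 of Table 6.1:1 all serve one aim: on- and off-treatment data are not to be mixed. A patient who finishes on Day 140 or 141 has, by definition, no follow-up phase. That is correct, but it does not settle the matter. Footnote D notes that Day 140 is on-treatment and stops there; no visible rule says where an assessment on that day is to be summarised. A flag or a separate row would keep the distinction without dropping the values.

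Second, little depends on Week 20. No hypothesis is tested, the primary endpoint is drug-related AEs, and the secondary efficacy endpoints are at Week 2. Individual values are listed, vital signs still enter the last, minimum and maximum on-treatment summaries, and N or the missing category shows the loss. AEs and plasma concentrations do not use these windows. All of this stands and limits the point to descriptive tables. GPPASI and GPPGA, however, have no stated summary to fall back on.

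Third, the size is conditional. Two of 8 days is not a share of patients. The drop in proportion needs a patient who was seen on Day 140 or 141, was GPPGA 0/1 and, outside the analysis that includes post-rescue values, had no earlier rescue. The real interval could widen or narrow, since the SD will change. This also stands.

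Fourth, the sections on further endpoints are largely missing from the public SAP, and its ADS plan is not available, so a display for late on-treatment values could exist there. That cannot be excluded, but nothing visible overrides Table 6.7:1.

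On first response, the last category is also labelled as Weeks 3 and 4, so a Week 4 visit value could be mapped into it. If that is the intent, the Day 28 limit needs rewording.

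**Conclusion.** The concern holds. As written, a protocol-compliant End-of-Trial assessment on Day 140 or 141 enters no Week 20 by-visit summary of GPPASI, GPPGA or vital signs, while later attendance is kept. Each case costs the amounts worked out above, which assume the section 7 denominator applies to the GPPGA proportion and, for the interval, an unchanged SD. The documents cannot show how many patients this touches.

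The change is worth making because the loss is avoidable and falls on patients seen on schedule. It is no more serious than that: the primary and Week 2 results do not depend on it. The first-response mismatch is real but smaller, and confined to agreement between two Week 4 displays.

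**What to change.** **Week 20 window.** Start the Visit 14 row of Table 6.7:1 at Day 140, set its planned day to 140, and relabel it Week 20 (End of Trial). Flag Day 140–141 values as within the REP. Revise footnotes C and D and the 6.6.2 sentence describing Visit 14 as follow-up to match. Leave Table 6.1:1 and the bar on imputing Visit 14 unchanged.

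If the split must be kept, show Day 140–141 values in a separate on-treatment Week 20 row. The SAP must then say that this row is not imputed, because 6.6.2 otherwise carries values forward to later on-treatment visits.

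**First response.** In 7.5.2.1, extend the last category to the end of the Week 4 window and state the period that no response covers. Add an after-Week-4 category only if the table is repeated at the final analysis.

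**Cost.** One window row and label, two footnotes, one sentence and one category list; no new data. The downside is that some Week 20 values will come from the last one or two days of the REP, hence the flag.

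**Timing.** The first-response edit belongs before the 4-week lock. SAP section 3 already foresees a later revision: "prior to the final DBL, updates will be required for the analyses of further endpoints related to biomarker and RNA sequencing data". The window change would be an added item there. Since it would follow the 4-week lock in an open-label trial, it should be recorded as such.
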